**C.8. Data Collection. (RQ-6, PC-2, PC-3)** Trained data collectors/interviewers who are employed by the Indiana University Center for Survey Research (CSR) will collect data via structured telephone interviews. Interviews will be conducted at baseline (T1), at 6 months post-baseline (T2), and at 9 months post-baseline (T3). If unable to reach participants when a phone interview is due, we will mail a letter to them requesting that they contact the CSR data collection team so that the interview may be completed. Reminder letters will be mailed to participants about 1 month before the T2 and T3 interviews are due. Process interviews will be conducted with participants assigned to the DVD intervention group approximately two weeks after mailing of the DVD. The baseline interview includes a question to confirm age eligibility and assesses the following: demographics, health literacy, health status, patient activation, CRC knowledge, CRC fear, cancer fatalism, colonoscopy-related procedural anxiety, social support, and media exposure. For both colonoscopy and FIT, the baseline interview asks questions about participants' experience with each test and readiness to screen by each test. Health beliefs for perceived CRC risk and colonoscopy and FIT perceived benefits, perceived barriers, and perceived self-efficacy are also collected. At completion of the baseline interview, participants will be randomized. People assigned to DVD or DVD + PN intervention groups will be told they will receive a DVD or instructions to access the website to view the program (based on their preference). Those in the tailored DVD + PN group will also be told they also will receive a phone call from the nurse navigator in about a week.

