## **SECONDARY OUTCOMES AND OTHER MEASURES (RQ-6, PC-3, IR-4)**

**Demographics, health literacy, health status, social support, and media exposure** will be assessed with items we have used in prior studies. Items will assess age, gender, marital/partnered status, number of persons living in the household, ethnicity, race, ethnic origin, education, employment, income, and insurance status. Additional items will assess health literacy, health status, comorbid conditions, and social support for having a colonoscopy. These items have been used for descriptive reporting in our previous research without interpretation or scoring difficulties. In the proposed study, questions about media exposure will assess previous exposure to information about CRC and colon testing.

**Colonoscopy-related procedural anxiety** will be measured using the 6-item short form of the State Anxiety Scale of the State-Trait Anxiety Inventory developed by Spielberger. This scale measures how an individual is feeling right now when thinking about having a colonoscopy. Validity and reliability have been widely reported and this scale has been commonly used in studies of colonoscopy-related anxiety.

**Perceived risk for CRC** will be assessed using two measures that consist of 5 items: a 4-item scale and a single item that assesses comparative age-adjusted risk. The summated risk scale was originally developed for breast cancer and adapted to CRC. Validity and reliability have been extensively tested with diverse population groups. Internal consistency reliability analyses from previous studies yielded Cronbach's alphas ranging from 0.75 to 0.79.

**CRC screening experience and readiness to screen** will be measured separately using 5 categorical items for colonoscopy and 6 categorical items for FIT. These items have been used in our prior studies to stage participants in terms of their readiness to uptake screening behaviors.

**Perceived Benefits** of FIT and colonoscopy will be respectively measured separately using the 3-item and 4-item summated scales used in our prior studies. Cronbach alpha coefficients obtained in preliminary studies were 0.72 for our 3-item benefits of stool testing scale and 0.69 for our 4-item colonoscopy benefits scale.

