**Table 5. Power Analyses**

Time/Test	PN plus DVD (n=115 at 9 mos)	DVD only (n=115 at 9 mos)	Usual Care (n=115 at 9 mos)	Power
9 month/ Any Test	44%	20%	5%	.80-.99

group). By 12 months, the 150 in each intervention group will decrease to 115 through an approximate 25% attrition. The multivariable logistic regression models for the intervention effect on the CRC screening completion outcome while accounting for covariates will very likely have greater than 80% power, more than for the bivariate models because a smaller sample size is required when

covariates are added to the model. In addition, this sample size will most likely ensure greater than 80% power for other outcomes of Aim 1 (quality of bowel preparation, anxiety, and satisfaction) because they are continuous or ordinal variables. Specifically, the analysis of continuous outcomes using a general linear model will have 99% power to detect a

small effect size of .50 standard deviation units between outcome means, and the ordinal logistic regression models will have more information than the binary models.

For Aim 2, our main interest is in whether the intervention effects differ by age, race, gender, and income. We consider this aim to be exploratory as we do not have preliminary data to estimate the effect sizes; however, we feel it is important to explore interactions in this study as they may identify subgroups of patients who may not need the more intensive support of a PN. For Aim 3, the revised sample size of 115 per group will allow for the detection of mediation effects with 80% power assuming the effect sizes from the intervention to mediator and from the mediator to outcome are moderate or higher (which is what is typically assumed in a power calculation). For Aim 3, to test mediation effects, we will use the percentile bootstrap method to estimate the indirect/mediated effect. Simulations of the two-path mediation model in Mplus (Table 2) show that 115 subjects per group are needed to have 80% power to test the total indirect effect using the Sobel approach when the effect of the independent variable (the intervention variable here) on the mediator is small (.2) and independent variable on outcome is medium (.39). Using the percentile bootstrap method instead of Sobel should afford the same or greater power.

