**C.13. Data Analyses. (IR-3, IR-5, MD-3, MD-5, HT-1, HT-2, HT-3, HT-4)** Preliminary analyses will compare baseline demographic information across groups using means and standard deviations for continuous variables and frequency distributions for categorical variables. We will adjust for those characteristics in subsequent analyses if significant differences emerge at a conservative level for inclusion of a covariate ( $p < .20$ ). Characteristics of participants who drop out by 9 months will be compared with those who remain to determine what biases may exist. **(MD-4)** The above analyses will be conducted using ANOVA, chi-square tests, or exact or non-parametric equivalents. If there appear to be biases in dropout, we will conduct pattern mixture models analyses to see how the results could change based on the MAR assumption **(IR-5, MD-2, MD-3, MD-5)**. Primary analysis of outcomes will employ an intent-to-treat analysis; all participants will be included regardless of compliance with interventions. The main outcome, CRC screening completion with any test (FIT or colonoscopy) will be extracted from medical records for all participants, including those who drop out or are lost to follow-up. Intervention exposure will be measured and its effects will be accounted for in the intent-to-treat analysis. First, we will know whether participants viewed none, part, or all of the DVD. Second, we will document how many contacts PNs make to or on behalf of participants assigned to that group. These variables (viewed none/part/ or all of the DVD and number of navigator contacts) will be added as covariates in analyses. For all aims, sensitivity analysis will be conducted as needed for each outcome to assess the effects of the model assumptions on the results **(IR-5)**. Assumptions, such as normality of residuals, will be checked and appropriate modifications to the analysis plan applied if needed, such as transformations or use of non-parametric methods. From our prior studies, we expect missing data to be minimal (less than 2%) for subjects during participation. For missing data on scales, we will use mean imputation as long as two-thirds of the questions have been answered (or per validated instrument instructions, if otherwise). **(MD-2, MD-3)**

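### Baseline readiness to screen and prior test experience are collected before randomisation but not named as covariates; fixing them in advance would be a cheap, modest improvement to the primary model

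*Combined protocol and SAP*

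**What the plan says.** **Collected before allocation.** In C.8, "the baseline interview asks questions about participants' experience with each test and readiness to screen by each test", the two tests being colonoscopy and FIT. The same section states: "At completion of the baseline interview, participants will be randomized". Under the secondary and other measures in C.9, these items "will be measured separately using 5 categorical items for colonoscopy and 6 categorical items for FIT", and earlier studies by the team used them "to stage participants in terms of their readiness to uptake screening behaviors".

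**Not used in allocation.** E.1 stratifies on sex, race/ethnicity and age only.

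**Adjustment text in C.13.** There are three pieces:
- A rule with a criterion: "Preliminary analyses will compare baseline demographic information across groups", followed by "We will adjust for those characteristics in subsequent analyses if significant differences emerge at a conservative level for inclusion of a covariate", at p < .20.
- Two exposure variables, extent of DVD viewing and number of navigator contacts, which are added as covariates. Both arise after randomisation.
- The primary Aim 1 model, a multivariable logistic regression of 12-month screening on group and unnamed participant characteristics, continuous or categorical, intended to adjust for possible confounders.

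**Power text in C.12.** The multivariable model is expected to have more than 80% power, "more than for the bivariate models because a smaller sample size is required when" covariates are added. No covariate is named.

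**The concern.** Of everything measured at T1, stage of readiness is conceptually closest to the primary outcome. The plan itself connects motivation with completion: under sample bias, C.14 worries that people already motivated to be screened will self-select into the trial.

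The only rule that says how a baseline variable gets into the model looks at demographics, and it selects on observed imbalance. Imbalance between randomised arms is chance and says nothing about prognosis. A balanced but strongly predictive variable would be passed over, while an imbalanced but irrelevant one would be included. Readiness is balanced only by chance, and whether it enters the model is left to a later decision.

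Two things are at stake: some precision on H1.1 and both H1.2 contrasts, and having the covariates of the primary model settled before outcomes are seen. C.12's expectation of extra power also depends on the covariates being predictive, which the stated rule does not ensure.

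**Working it through.** **1. Reproduce the plan's own power (Table 4).** Inputs from C.12: rates 44%, 20% and 5%; n = 115 per group; two-sided α = .05/3, so z = 2.394. Continuity-corrected chi-square, with d the difference in rates and p̄ their mean:

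power = Φ{[d − 1/n − z√(2p̄(1−p̄)/n)] / √[(p1(1−p1) + p2(1−p2))/n]}

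- 20% vs 5%: (0.15 − 0.0087 − 0.1044)/0.0425 = 0.87, giving 80.8% (stated 80%).
- 44% vs 20%: (0.24 − 0.0087 − 0.1473)/0.0594 = 1.41, giving 92.1% (stated 92%).
- 44% vs 5%: above 99.9% (stated 99%).

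Table 4 therefore stands with no covariates. Without the correction, the first two are 85.8% and 94.1%.

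**2. Add one prognostic baseline covariate at 115 per arm.** Logistic models were simulated with marginal rates held at the planned values. The likelihood-ratio test of arm at α = .05/3 was run with and without one standardised covariate (8,000 trials per setting, 4,000 at odds ratio 3). The odds ratio per SD is an assumption, because the documents give none.

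| Odds ratio per SD | 20% vs 5%: unadjusted → adjusted | 44% vs 20%: unadjusted → adjusted |
|---|---|---|
| 1.0 | 88.8% → 88.9% (+0.1) | 93.9% → 93.8% (0.0) |
| 1.5 | 88.7% → 89.4% (+0.7) | 94.2% → 94.9% (+0.8) |
| 2.0 | 88.5% → 90.4% (+1.9) | 94.5% → 96.2% (+1.6) |
| 3.0 | 88.0% → 92.0% (+4.0) | 94.1% → 97.8% (+3.7) |

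Gains were computed before rounding. The simulated unadjusted power is above Table 4 because the likelihood-ratio test has no continuity correction, so only the differences matter. A three-level readiness variable (assumed split 40/35/25%) gives a similar result for 20% vs 5%: 88.5% → 89.8% at an odds ratio of 2 per level and 88.6% → 91.6% at 3.

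**3. Repeat at 150 per arm.** C.13 takes the main outcome from medical records for everyone, including dropouts, so all 150 per arm may be analysable. A three-arm model with two readiness items and two yes/no experience items (3,000 trials per setting) was run at odds ratios of 1.5, 2 and 3 per level:
- 20% vs 5%: 96.3 → 96.3, 96.1 → 96.7, 96.0 → 96.8.
- 44% vs 20%: 98.7 → 98.7, 98.2 → 98.6, 98.6 → 99.5.

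The gain is 1 point or less throughout.

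**4. Smaller true effects.** C.12 first assumed 15.5% for the DVD arm. At 15.5% vs 5% with 115 per arm, power is 61% unadjusted, 64% at an odds ratio of 2 and 67% at 3. For 44% vs 28% with 150 per arm (the 28% is purely an assumption), it goes from 68.8% to 72.4% at an odds ratio of 2 and from 70.7% to 78.3% at 3.

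**5. Room for covariates.** Expected events at 115 per arm: usual care 0.05 × 115 = 5.75, or about 6; DVD 0.20 × 115 = 23; navigation plus DVD 0.44 × 115 ≈ 51. Eleven categorical items (5 + 6) could not sensibly enter one by one, so the readiness information must be condensed.

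**The case against.** The strongest reply is that C.13 does not exclude readiness. Its description of the primary model admits categorical and continuous participant characteristics without limiting them to demographics, and the readiness items fit that description. This stands. A reader might infer from the p < .20 rule that only demographics can ever be adjusted for, and that the trial is bound to forgo this information. The documents do not support that: the covariate set is unspecified, not restricted.

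Second, the gain is small at the planned rates, both contrasts are above 80% without it, and the prognostic strength is assumed. This also stands. The larger gains need effects smaller than planned, and the 44% vs 28% pair appears nowhere in the documents.

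Third, C.12's remark on covariate power is hedged, cites a methods reference that is not available here, and carries no weight in the sample size, which is justified on pairwise chi-square or bivariate logistic tests. A reader might take the remark as undermining the 115 per group; step 1 shows that it does not.

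Fourth, C.9 gives no scoring rule for these items and refers to fuller descriptions elsewhere, so a covariate would first have to be defined. That is a real but minor cost.

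What remains is that a primary model whose most outcome-relevant baseline variable may or may not be included is not prespecified. The post-randomisation exposure variables cannot fill that gap.

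**Conclusion.** The point holds as a free or cheap improvement of low priority. The items are valid pre-randomisation covariates, they are unnamed in the analysis plan, and the one explicit rule selects on imbalance instead of prognosis. C.12's claim of extra power is conditional on predictive covariates that the rule does not guarantee.

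Over assumed odds ratios of 1.5 to 3, the gain is about 0 to 4 points at the planned rates with 115 per arm and 1 point or less with 150. It is larger if true effects fall short of plan and zero if readiness does not predict screening. These figures assume a compact score that enters the model correctly. It would go too far to say that the trial is underpowered or that a planned conclusion is threatened.

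**What to change.** **C.13.** For the primary 12-month logistic model, replace selection on p < .20 imbalance with a short covariate list fixed in advance. Include one compact T1 readiness score for colonoscopy, one for FIT, and prior test experience, all kept whatever their observed imbalance. Take H1.1 and both H1.2 contrasts from that model. Define the scores before outcome data are examined, and state how prior FIT experience is coded for people recruited after a positive FIT (C.3). Keep the list short because of the roughly 6 expected usual-care events.

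**C.12.** Tie the statement on covariate power to these named predictors, and make clear that it holds only if they predict screening.

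**Cost.** A sentence or two in each section, a written scoring rule and a few degrees of freedom. No new data are needed, since the items are already part of the baseline interview. If readiness proves uninformative, step 2 shows essentially no loss for a single score.

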**Table 3: Data Collection Timeline**

Measures	Baseline Interview (T1)	Process Interview (2 weeks after mailing DVD)	Follow-up Interview at 6 months post-baseline (T2)	Final Interview at 9 months post-baseline (T3)	12 months post-baseline (Final medical record review)
Demographics, social support, media exposure	X				
Health literacy, health status to include co-morbidities	X				
CRC screening experience and readiness to screen, patient activation, health beliefs (perceived CRC risk, benefits of screening, barriers to screening, self-efficacy for screening), CRC fear, cancer fatalism	X		X		
Colonoscopy-related procedural anxiety	X		X	X	
CRC and screening knowledge	X		X		
Receipt, viewing and satisfaction with the DVD		X			
Receipt, experience & satisfaction with the PN			X		
Self-report of CRC screening intention and completion			X	X	
Satisfaction with the screening experience			X	X	
Trial participation feedback				X	
Medical record review: CRC screening test completion, quality of bowel preparation			X	X	X

**C.9. Measures.** The primary study outcomes of CRC screening completion with any test (FIT or colonoscopy), and quality of bowel preparation (for those who complete colonoscopy), colonoscopy-related procedural anxiety and satisfaction with the CRC screening experience are described in this section. Secondary outcomes of the interventions include changes in knowledge and health belief variables (perceived risk, benefits, barriers, and self-efficacy). Other measures include patient activation, CRC fear, cancer fatalism, and satisfaction with the interventions. Measures have been extensively tested and refined in preliminary studies, and are described in more detail elsewhere.

**PRIMARY OUTCOME MEASURES: (RQ-6, PC-2, IR-4)**

**Completion of any CRC screening test** (fecal immunochemical test (FIT) or colonoscopy) will be measured by medical record review. FIT and colonoscopy completion dates will be extracted from the electronic medical record. Because self-report of CRC screening has correlated well with medical record data, we will also use validated items from our previous research to ask participants if they have had a CRC screening test (FIT or colonoscopy) as well as their plan to have one in the next 6 months (only for those who have not yet completed screening).

**Quality of bowel preparation** will be assessed two ways for those participants who attend their colonoscopy: 1) by participant self-report of their bowel prep experience and 2) via review of electronic medical records. When patients arrive in the endoscopy department, a nurse assesses their experience with the bowel preparation and adherence to dietary restrictions. Patients who report they were unable to complete the bowel prep or have eaten in the past 24 hours are considered inadequately prepped for the procedure and sent home. These patients must repeat the preparation to cleanse the bowel and reschedule their colonoscopy. For those who report successful completion of the bowel prep and adherence to dietary restrictions, quality of the bowel preparation (i.e. degree of cleanliness/emptiness of the bowel) is evaluated by the endoscopist during the colonoscopy. Standard practice is to evaluate bowel preparation quality using an assessment similar to the Aronchick 5-point scale where 1=*excellent*, 2=*good*, 3=*fair*, 4=*poor*, and 5=*inadequate*. Adequate is a term that may also be used to describe the quality of bowel preparation as a single descriptor or in addition to the Aronchick assessment as excellent (1), good (2), or fair (3). Procedural notes including endoscopists' ratings of the quality of the bowel prep are entered into ProVation, a menu-driven software program. Therefore, participants will be considered inadequately prepped if they are: 1) deemed inadequately prepped from self-report during initial nursing assessment OR 2) if the endoscopist rates the quality of the bowel prep as poor (4)

or inadequate (5). Eskeanzi Health is introducing the Boston Bowel Preparation Scale (BBPS) as another type of bowel preparation quality measure. The BBPS measures quality on a 10 point scale of 0-9. BBPS evaluations will also be entered into ProVation by the endoscopist and compared to the Aronchick findings. A decision will be made at a later time as to whether or not the BBPS ratings will be included in reporting this study outcome.

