had a recent screening test. Improving CRC screening rates among racial/ethnic minorities has been identified as the first target to reducing these disparities.

**Patient-level barriers to CRC screening include low knowledge levels about CRC and CRC screening tests, perceptions of not being at risk for CRC, mistrust, fear of pain/discomfort, fear of finding cancer, embarrassment, unpleasantness of the bowel preparation.** Difficulty finding time, transportation difficulties, and costs of the tests have been identified as barriers to CRC screening by people with low incomes. Lack of social support has been identified as a barrier to CRC screening; family and friends who had negative experiences with screening tests can actively discourage participation. In a recent trial, the most common barriers to CRC screening were lack of knowledge about the test, fear, worry about test results and the bowel preparation. Inadequate bowel preparation is a major impediment to effective CRC screening with colonoscopy, and 25-30% of patients presenting for colonoscopy have not adequately cleansed, or emptied, their bowel. Suboptimal cleansing of the bowel leaves residual fecal matter that obscures polyps, leads to missed diagnoses, extends the time needed for the exam, and results in incomplete or aborted colonoscopies. This is a significant problem among patients in safety net health systems, where up to 30% of patients who do attend their colonoscopy appointment have not adequately cleansed their bowel. In addition, poor bowel preparation has been estimated to increase the cost of CRC screening by 22% in public hospitals due to patients needing to repeat colonoscopy or have another test earlier than suggested by current practice guidelines. Finding effective approaches to help patients who are willing to have a colonoscopy prepare for that test will reduce costs for patients and health systems, an especially important goal for those with limited resources.

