For Aim 1, we will test the primary hypothesis related to comparing intervention effects among the three randomized groups (H1.1: PN+DVD vs. DVD only and H1.2: PN+DVD vs. usual care and DVD only vs. usual care) using the outcome of completion of CRC screening using any test at 12 months post-baseline. In addition, quality of bowel preparation, procedural anxiety, and satisfaction with the screening experience will be examined as outcomes. As an initial assessment of CRC screening completion at 12 months, we will use a chi-square test for a 3 x 2 (group by screening completion) contingency table to test whether completion rates differ across groups. If the  $p$ -value for the overall test is significant at the .05 level, pair-wise 2 x 2 tests will be conducted at the  $.05/3 = .017$  level. However, the primary analyses for Aim 1 will involve fitting multivariable logistic regression models of the primary outcome of 12-month CRC screening test completion (yes/no). Independent variables will be group assignment and continuous and categorical individual characteristics. These models will also allow us to investigate intervention effects on CRC screening test completion while adjusting for potential confounders. Group assignment will be coded using dummy variables with usual care as the reference category. For H1.3, quality of bowel preparation will be analyzed for those participants who complete colonoscopy with proportional-odds ordinal logistic regression using an ordinal dependent variable ( $1 = \text{excellent}$ ,  $2 = \text{good}$ ,  $3 = \text{fair}$ ,  $4 = \text{poor}$ ,  $5 = \text{inadequate}$ ). If some outcome categories are sparse, the outcome will be dichotomized into adequate

(*excellent or good*) versus inadequate (*fair, poor, or inadequate*). The outcomes of anxiety and satisfaction are continuous outcomes and will be modeled with linear regression.

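### The primary endpoint sets no condition on bowel preparation or a full examination, and no all-randomised analysis shows how many people had an adequately prepared test

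*Combined protocol and SAP*

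**What the plan says.** - **Endpoint (C.9, Primary Outcome Measures).** Completion of FIT or colonoscopy comes from medical record review: "FIT and colonoscopy completion dates will be extracted from the electronic medical record". C.13 analyses it as "completion of CRC screening using any test at 12 months post-baseline".
- **Preparation (C.9).** A participant is inadequately prepared if the nurse's assessment before the procedure finds this, in which case the patient is sent home, or "if the endoscopist rates the quality of the bowel prep as poor (4") or inadequate (5).
- **Preparation analysis (C.13, H1.3).** "quality of bowel preparation will be analyzed for those participants who complete colonoscopy with proportional-odds ordinal logistic regression using an ordinal dependent variable", running from 1 (excellent) to 5 (inadequate).
- **Background (Section A).** Poor cleansing "leads to missed diagnoses, extends the time needed for the exam, and results in incomplete or aborted colonoscopies". In safety net systems, "up to 30% of patients who do attend their colonoscopy appointment have not adequately cleansed their bowel". The general figure is 25-30% of patients presenting. Repeat or earlier-than-guideline testing is mentioned in connection with cost.
- **Interventions (C.4.a, C.4.b).** The DVD gives preparation instructions, and navigators call 1-2 days before a colonoscopy to support preparation. H1.3 predicts better preparation with either intervention.

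**The concern.** Taken together, C.9 and C.13 imply that a colonoscopy the endoscopist rated poor or inadequate scores the same on the primary endpoint as a clean one. C.9 itself calls such a patient inadequately prepared. The documents do not say whether an aborted or incomplete examination receives a completion date, so record abstractors could decide this case by case.

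This matters for comparing arms because the interventions act on attendance and on preparation. Better preparation would make the gain in adequate screening larger than the gain in attendance. Bringing in more hesitant attenders could make it smaller. The any-test analysis cannot tell these apart. H1.3 cannot either, because it conditions on completing a colonoscopy, which happens after randomisation and is expected to differ sharply by arm.

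**Working it through.** **1. Size of the H1.3 groups.** Planned any-test rates (C.12, Table 4) times 115 analysed or 150 enrolled per arm:
- Usual care: 0.05 × 115 = 5.75; 0.05 × 150 = 7.5
- DVD: 0.20 × 115 = 23; 0.20 × 150 = 30
- DVD plus navigator: 0.44 × 115 = 50.6; 0.44 × 150 = 66

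These are ceilings, because some completers will have had FIT only. Usual care contributes at most about 6-8 colonoscopies to H1.3.

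**2. Reproducing Table 4.** Two-proportion normal approximation with continuity correction, two-sided α = 0.05/3 (z = 2.394):

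power = Φ[(|p1 − p2| − 1/n − z·SE0) / SE1], where SE0 = √(2p̄(1 − p̄)/n) and SE1 = √((p1(1 − p1) + p2(1 − p2))/n).

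DVD vs usual care, n = 115: (0.1413 − 2.394 × 0.0436)/0.0425 = 0.869, power 80.7% (Table 4: 80%). DVD plus navigator vs DVD: 92.1% (Table 4: 92%). DVD plus navigator vs usual care: above 99.9% (Table 4: 99%). The method matches the plan.

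**3. What the supportive analysis would cost in power.** Let q be the share of colonoscopies inadequately prepared (25-30%, Section A). Let f be the share of completers whose only test is a colonoscopy. The documents do not give f; it is assumed to be 50%. Each rate is multiplied by 1 − f·q, equally in all arms:
- q = 25%: factor 0.875, rates 38.5 / 17.5 / 4.4%
- q = 30%: factor 0.85, rates 37.4 / 17.0 / 4.25%

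| Comparison | n per arm | As planned | Supportive analysis |
|---|---|---|---|
| DVD vs usual care | 115 | 80.7% | 70.6-72.5% |
| DVD vs usual care | 150 | 91.9% | 84.7-86.2% |
| DVD plus navigator vs DVD | 115 | 92.1% | 83.1-85.0% |

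At 115 per arm, DVD vs usual care gives 76-77% for f = 25%, 64-68% for f = 75% and 58-62% for f = 100%. The 150 row is relevant because C.13 extracts the main outcome for everyone, including those who drop out.

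**4. If preparation differs by arm.** With an equal q, the DVD-to-usual-care ratio stays at 20/5 = 4.0. Assume instead 15% inadequate with DVD and 30% in usual care, with f = 50%. The rates are 0.20 × 0.925 = 18.5% and 0.05 × 0.85 = 4.25%, a ratio of 4.35, with power 79% at 115 and 91% at 150. Reversing the two shares gives 17.0% and 4.6%, a ratio of 3.7. Adequate screening can therefore move either way relative to attendance.

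**The case against.** This is an uptake trial in people who missed a colonoscopy. Any-test completion is a defensible primary endpoint, and the rates behind the power calculation come from trials tabulated on the same outcome (Tables 1 and 2). Preparation quality is a named outcome with its own hypothesis. That stands, and is why the primary endpoint should not change. Calling the main result something else would only be a preference of wording.

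Three stronger readings are tempting, and the documents do not support them:
- **That examinations rated 4 or 5 are always aborted or repeated.** Section A lists aborted examinations among several possible consequences, as background. The only mandatory repeat (C.9) covers patients sent home before any examination, who have no colonoscopy to count.
- **That the plan expressly counts aborted or poorly prepared examinations.** For rated ones this is an inference from the C.13 population. For aborted ones the plan is silent, and they may have no completion date.
- **That the trial loses power.** The planned test is unaffected. The lower figures belong to the added analysis, which has no power target. The 58-62% case needs every completer to have only a colonoscopy, which is unlikely when the DVD presents FIT and navigators mail kits.

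The 25-30% also overstates the share among examined patients, because the nurse's check removes some beforehand, and step 3 gives no credit for an adequate repeat or a later FIT.

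**Conclusion.** The concern holds as a gap in definition and a missing supportive analysis. It is not an error in the primary endpoint or the sample size. C.9 and C.13 imply that a colonoscopy rated poor or inadequate counts as completed; the classification of aborted or incomplete ones is unstated. Preparation is compared only in a subgroup formed after randomisation, with at most about 6-8 people in usual care at the planned rate. As planned, the trial can conclude on tests done by arm, but not on adequately prepared screening per person randomised.

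How far the two differ cannot be fixed from the documents. It depends on the colonoscopy share, on the inadequate share among those actually examined, and on whether that share differs by arm.

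**What to change.** 1. Keep the primary endpoint and sample size. Prespecify one supportive analysis in all randomised participants, with the same logistic model. Success is a completed FIT, or at least one colonoscopy by 12 months not rated poor or inadequate under C.9. An adequate repeat or a later FIT then still counts.
2. State how aborted and incomplete examinations are classified, for the primary and the supportive analysis.
3. Reconcile the cut-off first. C.9 allows fair (3) to be described as adequate, while the C.13 fallback for sparse categories groups fair with inadequate. Also say how a note reading only adequate is handled, and whether Boston scale ratings are used, since C.9 leaves that for later.

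**Cost.** One extra model. Table 3 already has preparation quality extracted at 6, 9 and 12 months. Table 3 does not list procedure extent or abortion, so a little extra abstraction may be needed. The supportive analysis will have fewer events and lower power, as shown above.
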